#### 4. ANALYSIS POPULATIONS

##### Screened Population

The screened population will include all screened patients who signed the informed consent.

##### Randomized Population

The randomized population will include all randomized patients irrespective of patient receiving any study drug. The treatment group assignment in this population will be defined by the treatment planned as per the initial randomization schedule.

##### Safety Population

The safety population will include all randomized patients who receive at least 1 dose of study drug. The treatment group assignment in this population will be defined by the treatment actually received. This population will be used for the analysis of safety.

##### Intention-to-Treat Population

The intent-to-treat (ITT) population will include all randomized patients who received at least one dose of study medication irrespective of any deviation from the protocol or premature discontinuation. The treatment group assignment will be designated according to initial randomization. The ITT population will serve as the basis for the analysis of efficacy.

##### Per Protocol Population

The per-protocol (PP) population is a subset of the intent-to-treat population. The per-protocol population consists of all patients who do not violate the terms of the protocol in a way that would impact the study outcome significantly, as determined by the Medical Monitor who is blinded to study drug assignment. All decisions to exclude patients from the per-protocol population dataset will be made prior to the unblinding of the study.

Analyses using the per-protocol population may be provided as a sensitivity analysis.

#### 5. DEFINITIONS AND DERIVED VARIABLES

Study Start Date, Study Stop Date, and Duration: Study start date for a given patient is defined as the date of screening and study stop date is defined as the date on which the patient end of study form was completed at the end of study. Study duration is defined as (study stop date – study start date) + 1 in days.

Baseline: Baseline for all safety and efficacy measurements will be defined as the last assessment prior to study drug administration unless stated otherwise.

Study Day: Study day will be calculated by subtracting date of first dose date i.e. day 1 from respective event date. Day 1 is the date of the first dose of study drug.

Study day= Event date – Day 1 date.

Study day= Event date – Day 1 date + 1 (For those events occurring on or after Day 1).

Modified UCDAI Score: The modified UCDAI score will be computed as combined score of stool frequency, rectal bleeding, mucosal appearance, and the physician's global assessment.

Sigmoidoscopy Score: It is the “mucosal appearance” score which is collected at visit 3 and 6 along with Rectal Bleeding, Stool Frequency and Physicians Global Assessment.

## 6. STATISTICAL CONSIDERATIONS

For efficacy and safety data, descriptive statistics (n, mean, standard deviation [SD], median, minimum, and maximum for continuous data, and n [%] for categorical data) will be presented. Similarly, wherever applicable, changes from baseline will be summarized in the same manner.

Unless otherwise stated, the denominator for percentages will be based on the number of patients in each treatment group who provided non-missing responses to the categorical variable, all statistical tests will be two-sided and at the 5% level of significance, and all differences between treatment groups will be presented with two-sided 95% confidence intervals (CIs). All p-values will be displayed to three decimals and rounded using standard scientific notation (e.g., 0.XXX). If a p-value less than 0.001 occurs it will be shown in tables as <0.001. If a p value greater than 0.999 occurs it will be shown in the tables as >0.999.

Unless otherwise stated, percentages will be presented to one decimal place in all summaries.

Minimum and maximum values will be presented to the same number of decimal places as collected on the case report form (CRF) or within the laboratory panel; mean and median will be presented to one decimal place more than CRF data; standard deviation will be presented to two decimal places more than CRF data.

Dates will be presented in format DDMMYY and numbering for tables, figures, and listings will follow ICH E3.

All statistical analyses will be performed using Statistical Analysis System (SAS®) version 9.4 or higher (SAS Institute, Cary, NC).

## 7. METHODS OF ANALYSES AND PRESENTATIONS

### 7.1 Patient Disposition

The number of patients screened and the number of screen failures at Visits 1 (screening), 2 (baseline visit), and 3 (randomization) will be summarized overall. The number of randomized patients will be presented by treatment and overall, and the number and percentage of randomized patients who were treated, completed the study, and discontinued (along with the primary reason for discontinuation) will also be presented by treatment group and overall.

The number and percentage of randomized patients in the safety, ITT, and PP populations will be summarized by treatment group and overall.

Data including screen failures, inclusion/exclusion criteria evaluation, randomization details, patients randomized but not treated, and protocol deviations or violators will be listed. Patient's analysis population will be listed.

### 7.2 Protocol Deviations

Protocol deviations are deviations that occurred before or during the randomized treatment period. Protocol deviations will be recorded from the screening visit. The following criteria are considered as major protocol deviations:

- Patient did not satisfy all inclusion/exclusion criteria.
- Patient was unblinded to the study treatment or if treatment code is broken by site without medical emergencies of patient.
- Treatment compliance is not in the range of 80% to 120%.
- Patient took concomitant medication during the study which was forbidden in the protocol.
- Patient is treated with any other study medication in another clinical study.

- Missing primary efficacy data at baseline and the end of treatment visit.

Protocol deviations will be identified at the study site and recorded in an Excel spreadsheet by a sponsor representative and shared with the inVentiv Health Clinical statistical programming team before database lock.

The number and percentage of ITT patients experiencing at least one major protocol deviation and the number and percentage of ITT patients with each type of major protocol deviation will be summarized by treatment group and overall.

All protocol deviations will be listed.

### **7.3 Demographic and Baseline Characteristics**

The demographic and baseline characteristics will include age, gender, female childbearing potential status, ethnicity, race, smoking history, height, body weight, and body mass index (BMI). Demographic and baseline characteristics will be summarized using descriptive statistics for each treatment group and overall for the safety population.

BMI is derived using weight and height collected at the screening visit (Visit 1) and is computed as (weight (kg) / [height (m)]).

All demographic and baseline characteristics will be listed by treatment group, site number, and patient number.

### **7.4 Medical History**

Medical history will include any significant conditions or diseases that stopped at or prior to screening (time of informed consent) or are present and stable at screening. Medical history conditions will be coded using the Medical Dictionary for Regulatory Activities (MedDRA) coding system Version 17.0 or higher.

A summary table of medical history conditions by system organ class and preferred term will be presented for each treatment group and overall. The table will be sorted in alphabetical order by system organ class and in alphabetical order of preferred terms within each system organ class. The frequency and percentage of patients who present at least one occurrence of the system organ class or preferred term will be presented by treatment group and overall. The denominator

used for calculating the percentages will be the total number of patients included in the safety population for each treatment group. All medical history conditions will be listed.

### **7.5 Prior and Concomitant Medication**

Prior medication is defined as any medication starting and ending before the first dose of study medication. Concomitant medication is defined as any medication, other than the study medication, that either started before the first dose of study medication and continued into the double-blind treatment period, or that started after the first dose of study medication. If based on available start and stop date information it cannot be determined whether a medication use is prior or concomitant, the medication use will conservatively be assumed concomitant.

Prior and concomitant medications will be classified using the World Health Organization Drug Dictionary (WHO-DD) March 2014 and will be summarized separately by treatment and overall, giving the number and percentage of patients by Anatomical Therapeutic Chemical (ATC) Level 2 and 4 code and preferred term. Patients will be counted only once at a given level if they had more than one concomitant medication use at the level. The table will be sorted in alphabetical order first by ATC Classification Level 2, then by ATC Classification Level 4, and then in decreasing frequency of preferred WHO names based on total number of patients within each combination of ATC classification levels. The denominator used for calculating the percentages will be the total number of patients included in the safety population for each treatment or overall.

All prior/concomitant medications will be listed.

### **7.6 Concomitant Procedures**

Concomitant procedures includes all treatments taken during the effective duration of study treatment, whether or not they are recorded at baseline (i.e., have stop day greater than or equal to Day 1).

The concomitant procedures will be classified using the MedDRA coding system and will be summarized for the safety population by treatment group and overall as the number and percentage of patients by system organ class and preferred term (or higher level term, if no preferred term is available). Patients will be counted only once at each level of summarization if they are receiving more than one concomitant procedure at that level.

All concomitant procedures will be listed.

### **7.7 Study Drug Exposure and Compliance**

Duration of exposure, in days, will be calculated for each patient as the date of the last dose of study medication minus the date of the first dose of study medication, plus 1 day. Duration of exposure will be summarized descriptively by treatment group and overall for the safety population.

In general, percent dosing compliance for an individual patient will be computed as:

$$(\text{number of capsules taken}) / (\text{number of capsules expected to be taken}) \times 100\%$$

Percent dosing compliance between two visits will be computed where:

$$\text{number of capsules taken} =$$

- number of capsules dispensed at the earlier visit
- number of capsules returned (from those dispensed at the earlier visit)
- number of capsules reported lost/damaged (of those dispensed at the earlier visit)

and

$$\text{number of capsules expected to be taken} =$$

$$(\text{date of the later visit} - \text{date of the earlier visit} [+1 \text{ if the earlier visit is Visit 3}]) \times 6$$

Percent dosing compliance for the whole study will be computed where:

$$\text{number of capsules taken} =$$

- number of capsules dispensed at all visits
- number of capsules returned at all visits
- number of capsules reported lost/damaged at all visits

and

$$\text{number of capsules expected to be taken} =$$

$$(\text{date of the last visit} - \text{date of the first dose} + 1) \times 6$$

Percent dosing compliance will be summarized descriptively at Visits 4, 5, and 6, and for the study as a whole, by treatment group and overall for the safety population. Dosing noncompliance is defined as taking less than 80% of study medication capsules during the whole treatment period. Overall dosing compliance and by visit dosing compliance will be categorized as <80%, 80% to 100%, and >100%, and summarized descriptively by treatment group and overall for the safety population.

All study drug administration, accountability, and compliance data will be listed.

## 7.8 Efficacy Data Endpoints and Analyses

All efficacy endpoints will be analyzed for both the ITT population (the primary analysis population) and PP population. Comprehensive listings of all efficacy data will also be presented.

### 7.8.1 Primary Efficacy Endpoint

The primary efficacy endpoint is the percentage of patients in remission at Week 6. A patient is considered to be in remission (a responder) at Week 6 if the patient has a modified UCDAI score of  $\leq 1$ , with a score of 0 for rectal bleeding and stool frequency, no mucosal friability (a mucosal appearance score of  $\leq 1$ ), and sigmoidoscopy (mucosal appearance) score not exceeding 1. A patient is considered to be a non-responder if no diary data is available within the period from Day 36 to study end or endoscopy within the period from Day 28 to study end (a non-responder imputation approach).

The number and percentage of patients who are in remission at Week 6 will be presented by treatment group, along with 95% confidence intervals constructed using the Clopper-Pearson method.

The percentage of patients in remission at Week 6 will be compared between each of the IBD98-M groups and placebo using Fisher's exact test. Each test will be 2-sided and declared statistically significant at the 0.05 level. No adjustment will be made for the two comparisons.

A bar chart of the percentage of patients in remission at Week 6 for each of the two IBD98-M groups and placebo will be presented.

As a supportive analysis, the primary efficacy endpoint will also be analyzed using the per protocol population.

Also, a sensitivity analysis will be used to assess the effects of missing data. The primary efficacy endpoint will be analyzed on the ITT population without making use of the non-responder imputation approach. Similar statistical methods will be used for the sensitivity analysis as is to be used for the primary efficacy analysis on the ITT population (which will use a non-responder imputation).

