	
endoscopy subscore. In addition, the diagnosis of UC must be confirmed by endoscopic and histologic evidence in the past; if prior confirmation is not available, this must be done at the time of screening endoscopy. After the screening visits, eligible patients will be randomized to 1 of 3 study groups: (1) IBD98-M 0.8 g/day (mesalamine 0.8 g with sodium hyaluronate 92 mg), (2) IBD98-M 1.2 g/day (mesalamine 1.2 g with sodium hyaluronate 138 mg), or (3) placebo. Up to 51 patients will be enrolled in this study (including drop-out patients), with 17 patients randomized to each treatment group. Patients will be encouraged to take their medication at the same time every day.
 
During the study, patients will visit the clinic on 7 occasions: 2 visits during the screening period (the second screening visit is the baseline visit); 4 visits during the treatment period at Weeks 0, 2, 4, and 6; and 1 visit at the end of the follow-up period at Week 8 (end of study/withdrawal visit). Patients will record the dates/times of dosing (after randomization), concomitant medication, and AEs in a daily diary starting 7 days before treatment and continuing until the end of study/withdrawal visit.
 
Rescue medication will not be permitted during the 6 weeks of the treatment period, and patients who are considered to not be benefiting from the therapy can be withdrawn and assigned an appropriate alternative UC treatment by the Investigator. Compliance will be assessed throughout the study by determining the amount of unused medication. Records will be kept of all medication dispensed, used, and returned by each patient. At the end of the study, all unused trial medication and used packaging will be returned to the Sponsor. All study medication will be accounted for and any discrepancies documented.

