### **7.3 Withdrawal, Removal, and Replacement of Patients**

At any time, a patient's participation in the study may be terminated at his/her request or on the basis of the Investigator's clinical judgment. The reason for patient withdrawal will be noted on the electronic case report form (eCRF).

A patient may be discontinued from the study for the following medical or administrative reasons:

- Occurrence of an AE that in the judgment of the Investigator suggests an unacceptable risk to the patient
- Development of any condition on-study that, in the opinion of the Investigator or the Sponsor, places the patient at an unacceptable medical risk if he/she continues
- Pregnancy
- Patient request
- Institution of additional medical (rescue) therapy for UC. Rescue medication will not be permitted during the 6-week double-blind treatment period, and patients considered as treatment failures will be withdrawn and assigned an appropriate alternative UC treatment by the Investigator.

The Investigator may discontinue individual patients from the study at any time. Patients will be encouraged to complete the study; however, they may voluntarily withdraw at any time. The date of and reason for study discontinuation must be recorded on the eCRF regardless of the reason for withdrawal; all patients will be asked to undergo an end-of-study/early termination evaluation. Every attempt will be made to obtain all of the end-of-study assessments, including all of the subscales

of the UCDAI (i.e., stool frequency, bleeding, physician's assessment, and sigmoidoscopy score).

This study may be terminated at the discretion of the Sponsor or any regulatory agency. An Investigator may elect to discontinue or stop the study at his or her site for any reason, including safety or low enrollment.

In the event that a patient discontinues prematurely from the study due to a TEAE or serious TEAE, the TEAE or serious TEAE will be followed until it resolves (returns to normal or baseline values) or stabilizes, or until it is judged by the Investigator to be no longer clinically significant.

Patients who withdraw or are withdrawn may not re-enter the study and will not be replaced under this protocol.

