### **8.6.3 Prior and Concomitant Medications**

Patients must follow the medication restrictions outlined in the inclusion and exclusion criteria (Sections 7.1 and 7.2) during the study. The use of hormonal contraceptives will be allowed and documented. Any concomitant medication use other than the occasional use of acetaminophen will be evaluated on a case-by-case basis by the Investigator. All concomitant medication use will be documented.

The use of the following medications is prohibited during the study:

- Rectal 5-ASA, budesonide, or steroids
- Systemic (oral or intravenous [IV]) corticosteroid
- Oral or parenteral immunosuppressants for treatment of UC
- Antibiotics for treatment of UC

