#### **12.4.1 Analysis of Efficacy Endpoints**

The primary analysis will utilize the ITT population, with non-responder imputation. A subject is considered a non-responder if no diary data is available within Day 36 to study end or endoscopy within Day 28 to study end. Remission will be assessed, defined by a UCDAI score of  $\leq 1$ , with a score of 0 for rectal bleeding and stool frequency, no mucosal friability, and  $\geq 1$  point reduction from baseline in the sigmoidoscopy score. Proportion rates between groups will be summarized with 95% confidence intervals included. Treatment groups will be compared using analysis of variance (ANOVA).

As a supportive analysis, the primary analysis will also be done using the per protocol population. Also, sensitivity analysis to assess the effects of missing data may be performed.

Secondary endpoints corresponding to remission or improvement will be analyzed in a manner similar to the primary endpoint. No adjustments for multiplicity will be made.

Secondary safety endpoints will be listed and summarized by treatment group.

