## **10. HANDLING OF MISSING VALUES AND OUTLIERS**

A non-responder imputation approach will be used for the primary efficacy endpoint data (see details in Section 7.8.1 of this SAP). No imputation will be done for secondary and exploratory endpoints. Missing data handling approaches for AE are in Section 7.9.1.

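### The primary responder rule says nothing about prohibited or alternative UC therapy, so a patient who takes it, stays to Week 6 and meets the criteria counts as a remission; one sentence in SAP 7.8.1 would close the gap

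*SAP*

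**What the plan says.** SAP 7.8.1 makes a patient a responder if the Week 6 modified UCDAI total, the bleeding and stool-frequency scores and the mucosal score meet the stated limits. One imputation follows: "A patient is considered to be a non-responder if no diary data is available within the period from Day 36 to study end". The same status is given when the patient lacks a sigmoidoscopy from Day 28 onward. Protocol 12.4.1 has the same rule, and SAP section 10 only refers back to it: "A non-responder imputation approach will be used for the primary efficacy endpoint data".

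The ITT population (SAP section 4) keeps every dosed patient regardless of deviation or early discontinuation. SAP 7.2 lists this among the major deviations: "Patient took concomitant medication during the study which was forbidden in the protocol". It attaches no consequence for responder status.

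On conduct, protocol 7.3 bars rescue medication during the treatment period and says that "patients considered as treatment failures will be withdrawn and assigned an appropriate alternative UC treatment by the Investigator". The synopsis also bars rescue but says that patients not benefiting "can be withdrawn and assigned an appropriate alternative UC treatment". Protocol 8.6.3 lists drugs prohibited on study, among them "Rectal 5-ASA, budesonide, or steroids", and carries the medication restrictions of Sections 7.1 and 7.2 into the study period.

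**The concern.** The protocol calls patients moved to other UC therapy treatment failures, yet no analysis rule says so. If such a patient has diary and endoscopy data in the windows and meets the criteria, the remission is credited to the randomized arm even though another drug may have produced it. The primary objective is to compare remission on each dose with placebo, in arms of 17, so a single patient of this kind is visible in the result. If the handling is not fixed before unblinding, it could be chosen once its effect on the comparison is known.

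**Working it through.** **Inputs.** 17 per arm, placebo rate 0.20 and target difference 0.18, hence 0.38 on the best arm (SAP 3.3). Two-sided Fisher's exact test at 0.05, each dose against placebo, unadjusted (SAP 7.8.1). Imputation windows: diary from Day 36, endoscopy from Day 28, both to study end. Use of other UC therapy: not given in the documents.

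**The plan's own figure.** With true rates 0.20, 0.20 and 0.38, the exact binomial probability that the best arm ranks first (ties split at random) is 0.790 at 16 per arm and 0.800 at 17. The stated 17 is reproduced and does not depend on this point. The exact Fisher power for 0.38 v 0.20 at 17 per arm is 0.117.

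**Who is exposed.** Reading the rule so that absence of either item gives non-response:

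- Takes a forbidden UC drug, stays in, has Visit 6 data: scored as observed, and a responder if the criteria are met.
- Withdrawn before Day 36, diary stopped: non-responder, because there is no diary data from Day 36. An endoscopy before Day 28 also falls outside its window.
- Withdrawn on or after Day 36, or diary continued, with an endoscopy from Day 28: scored as observed. Protocol 7.3 asks for every UCDAI subscale at withdrawal, including sigmoidoscopy, so the data may exist.
- Fails the UCDAI criteria, whatever was taken: non-responder.

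The first group is the main exposure; the third is small.

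**Size per patient.** 1/17 = 5.9 percentage points, and 5.9/18 = 0.33 of the target difference.

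**Effect on the test (active v placebo).**

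| Counts | Two-sided Fisher p |
|---|---|
| 10/17 v 3/17 | 0.032 |
| 10/17 v 4/17 | 0.080 |
| 9/17 v 3/17 | 0.071 |
| 6/17 v 3/17 | 0.438 |
| 6/17 v 4/17 | 0.708 |

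From 10/17 v 3/17, one added placebo remission loses significance. From 9/17 v 3/17, one added active remission gains it. But 10/17 v 3/17 is a gap of 7/17 = 41 points, far above the planned 18. The expected counts are 17 × 0.38 = 6.5 and 17 × 0.20 = 3.4; near them no conclusion changes. To see how often one patient matters, sum the binomial probabilities at 0.38 v 0.20 over all outcomes that are significant in favor of active drug but not after one more placebo remission. The total is about 0.07, given that one such placebo patient exists.

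**Direction.** Suppose a fraction f of an arm's non-remitters take other therapy and remain assessable, and a fraction r of those then meet remission. The observed rate is p + (1 − p) × f × r. Assumed ranges: f from 5% to 20%, r from 30% to 50%. All four cases below use r = 50%.

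- f = 20% placebo, 10% active: 0.20 + 0.80 × 0.20 × 0.50 = 0.280; 0.38 + 0.62 × 0.10 × 0.50 = 0.411; difference 0.131.
- f = 10% placebo, 20% active: 0.20 + 0.80 × 0.10 × 0.50 = 0.240; 0.38 + 0.62 × 0.20 × 0.50 = 0.442; difference 0.202.
- Extremes of the assumed range: 20% placebo, 5% active gives 0.3955 − 0.280 = 0.116; 5% placebo, 20% active gives 0.442 − 0.220 = 0.222.

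The planned 0.18 can shrink or grow.

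**The case against.** The strongest reply is that the design already closes most of the route. Rescue is barred, treatment failures are to be withdrawn, and withdrawal before Day 36 with the diary stopped leads to non-response through missing data. Someone judged a failure after Day 36 would still have to show no bleeding, normal stool frequency and a mucosal score of at most 1. This stands, so a reader should not infer that rescued patients generally count as successes, or that missing data is the only way to be a non-responder; failing the criteria is the ordinary way.

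A second reply is that observed scoring in ITT with a supportive per-protocol analysis is a coherent treatment-policy approach, and that forbidden medication is tabulated by arm. That is fair in principle, but the SAP does not state this intention. Its one sensitivity analysis concerns missing data. Per-protocol exclusion rests on the blinded Medical Monitor's judgment, is not expressly tied to the major-deviation list, and removes the patient instead of counting a failure.

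Two further inferences are not supported. One is that the on-study prohibited list leaves out the drugs named only in exclusion 9; protocol 8.6.3 cross-refers to Sections 7.1 and 7.2. The other is that the bias must run toward no difference; the documents give no usage by arm.

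Finally, the SAP is based on Protocol Amendment 3 and cites a Section 7.4 that the protocol reviewed here lacks. The withdrawal wording should therefore be checked against that amendment.

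**Conclusion.** The gap is real but narrow, and closing it is a cheap improvement. As written, a patient who takes prohibited or alternative UC therapy, has diary and endoscopy data in the windows and meets the Week 6 criteria is a remission in the assigned arm. This affects mainly patients who take a forbidden drug and remain to Visit 6, plus a few withdrawn late.

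Each such patient is worth 5.9 points in one arm. Their number is unknown, and the shifts in the difference shown above rest on assumed usage. The bias dilutes the effect if the use is on placebo and inflates it if on active drug. The p-value reversal at 10/17 v 3/17 shows what one patient can do near the significance boundary; it is not the expected outcome, as the figure of about 7% makes clear. The sample size is unaffected.

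**What to change.** Add to SAP 7.8.1 that a patient who receives protocol-prohibited or alternative UC therapy, or is withdrawn as a treatment failure, before the Week 6 assessments is a non-responder in the primary analysis. Keep the present observed scoring as a sensitivity analysis. This fits the non-responder approach already in the plan and the protocol's own description of these patients.

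Reconcile the withdrawal wording of the synopsis with that of protocol 7.3 against the current amendment, so that withdrawal as a treatment failure has one meaning in the analysis. Which wording is right is for the sponsor to decide; no change to clinical care is proposed.

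The cost is one sentence and one sensitivity table, from concomitant medication data already recorded at every visit. The downside is that a few remissions on other therapy are scored as failures, which the sensitivity analysis would show. The change should be made before unblinding.
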